1.1 Disposition of Subjects

1.1.1 Study Information (Part A and Part B)

Analysis Set:	All Subjects Who Signed the Informed Consent Form
Analysis	
Variable(s) :	Date First Subject Signed Informed Consent Form
	Date of Last Subject's Last Visit/Contact
	MedDRA Version
	WHO Drug Version
	SAS Version Used for Creating the Datasets
Analytical	
Method(s):	(1) Study Information
	Study information shown in the analysis variables section will be provided.

1.1.2 Screen Failures

Analysis Set:	All Subjects Who Did Not Enter the Treatment Period	
Analysis		
Variable(s) :	Age (years)	[Min<= - <=64, 65<= - <=74,
		75<= - <=Max]
	Gender	[Male, Female]
Analytical		
Method(s):	(1) Screen Failures	
	Frequency distributions for categorical variables and descriptive statistics for	

continuous variables will be provided.

1.1.3 Subject Eligibility

Analysis Set:	All Subjects Who Signed the Informed	Consent Form
Analysis	Eligibility Status	[Eligible for Entrance into the
Variable(s) :		Treatment Period, Not Eligible for
		Entrance into the Treatment Period]
	Primary Reason for Subject Not	[Pretreatment Event/Adverse Event,
	Being Eligible	Major Protocol Deviation, Lost to
		Follow-Up, Voluntary Withdrawal,
		Study Termination, Did Not Meet
		Entrance Criteria, Other]
Analytical		

Method(s): (1) Eligibility for Entrance into the Treatment Period
 Frequency distributions will be provided. When calculating percentages for
 the primary reasons for subject not being eligible, the total number of
 ineligible subjects will be used as the denominator.

1.1.4 Number of Subjects Who Entered the Treatment Period by Site and Treatment Group

Analysis Set:	All Subjects Who Entered the Treatment Period	
Analysis		
Variable(s) :	Status of Entrance into	the [Entered]
	Treatment Period	
Stratum:	Site	[Site numbers will be used as categories]
Analytical		
Method(s):	(1) Number of Subjects Who	o Entered the Treatment Period by Site and
	Treatment Group	
	Frequency distribution will be	e provided for each stratum by treatment group
	and overall.	

Analysis Set:	All Subjects Who Entered the Treatment Period	
Analysis		
Variable(s) :	Study Drug Administration Status	[Eligible but Not Treated]
	Reason for Not Being Treated	[Pretreatment Event/Adverse Event,
		Major Protocol Deviation, Lost to
		Follow-Up, Voluntary Withdrawal,
		Study Termination, Lack of Efficacy,
		Other]
	Study Drug Completion Status	[Completed Study Drug, Prematurely
		Discontinued Study Drug]
	Reason for Discontinuation of	[Pretreatment Event/Adverse Event,
	Study Drug	Major Protocol Deviation, Lost to
		Follow-Up, Voluntary Withdrawal,
		Study Termination, Lack of Efficacy,
		Other]
	Completion Status of the Safety	[Completed Safety Follow-up,
	Follow-up	Prematurely Discontinued Safety
		Follow-up]
	Reason for Discontinuation of the	[Pretreatment Event/Adverse Event,
	Safety Follow-up	Major Protocol Deviation, Lost to
		Follow-Up, Voluntary Withdrawal,
		Study Termination, Lack of Efficacy,
		Other]

1.1.5 Disposition of Subjects

Analytical

Method(s): (1) Disposition of Subjects

Frequency distributions will be provided for each treatment group and overall. When calculating percentages for the reasons for not being treated, the total number of subjects not treated by the study drug will be used as the denominator. When calculating percentages for the reasons for discontinuation of study drug, the total number of subjects who prematurely discontinued the study drug will be used as the denominator. When calculating percentages for the reasons for discontinuation of the safety follow-up, the total number of subjects who prematurely discontinued the safety follow-up will be used as the denominator.

1.1.6 Protocol Deviations and Analysis Sets

1.1.6.1 Protocol Deviations

Analysis Set: All Subjects Who Entered the Treatment Period

Analysis

Protocol Deviation	[Major GCP Violations, Deviations of Protocol
	Entry Criteria, Deviations of Discontinuation
	Criteria, Deviations Related to Treatment
	Procedure or Dose, Deviations Concerning
	Excluded Medication or Therapy, Deviations to
	Avoid Emergency Risk]
	Protocol Deviation

Analytical

Method(s): (1) Protocol Deviations

Frequency distribution will be provided by treatment group and overall for each deviation category. A subject who has several deviations will be counted once in each appropriate category. A subject who has several deviations that can be classified into the same category will be counted only once.

1.1.6.2 Analysis Sets

Analysis Set:	All Subjects Who Entered the Treatment Period	
Analysis Variable(s) :	Handling of Subjects and Subject Data	[Categories are based on the specifications in Handling Rules for Analysis Data]
	Analysis Sets	
	Full Analysis Set	[Included]
	Safety Analysis Set	[Included]
	DLT Analysis Set	[Included]
	Pharmacokinetic Analysis Set	[Included]
Analytical		
Method(s) :	(1) Subjects Excluded from Analysis Sets	
	(2) Subject Data Excluded from Analysis Sets	
	(3) Analysis Sets	
	Frequency distributions will be provided by treatment group for (1) and (2)	
	and by treatment group and overall for (3) . For (1) and (2) , a subject who has	
	several reasons for exclusion will be counted once in each appropriate	
	category. A subject who has several reasons for exclusion that can be	
	classified into the same category will be counted only once.	

1.2 Demographics and Other Baseline Characteristics

1.2.1 Summary of Demographics and Other Baseline Characteristics

Analysis Set: Safety Analysis Set Analysis Variable(s) : Age (years)

Age (years)	[Min<= - <=64, 65<= - <=74,
	75<= - <=Max]
Gender	[Male, Female]
Height (cm)	
Weight (kg) (Week 0)	
BMI (kg/m^2) (Week 0)	
Smoking Classification	[The subject has never smoked,
	The subject is a current smoker,
	The subject is an ex-smoker]
ECOG Performance Status (Week	[0, 1, 2, 3, 4]
0)	
Diagnostic Method	[Histological Diagnosis, Cytological
	Diagnosis, Other]
Disease Duration (days)	
Gleason Grading System (Gleason	[2, 3, 4, 5, 6, 7, 8, 9, 10]
Score)	
Histologic Type	[Adenocarcinoma, Other]
Degree of Differentiation	[Well Differentiated
	Adenocarcinoma, Moderately
	Differentiated Adenocarcinoma,
	Poorly Differentiated
	Adenocarcinoma,
	Unclassified Adenocarcinoma]
TNM Classification T	[T0, T1, T2, T3, T4, TX]
TNM Classification N	[N0, N1, NX]
TNM Classification M	[M0, M1, MX]
Prostatectomy	[Yes, No]
Radical Prostatectomy	[Yes, No]
High-Intensity Focused Ultrasound	[Yes, No]
Radiation Therapy	[Yes, No]
Other Treatment	[Yes, No]
PSA (ng/mL) (Week 0)	
Testosterone (ng/mL) (Week 0)	

Analytical

Method(s) :(1) Summary of Demographics and Baseline CharacteristicsFrequency distributions for categorical variables and descriptive statisticsfor continuous variables will be provided by treatment group and overall.

1.2.2 Medical History and Concurrent Medical Conditions

Analysis Set:	Safety Analysis Set
Analysis	
Variable(s) :	Medical History
	Concurrent Medical Conditions
Analytical	
Method(s) :	(1) Medical History by System Organ Class and Preferred Term
	(2) Concurrent Medical Conditions by System Organ Class and Preferred
	Term
	Frequency distributions will be provided for each treatment group and
	overall. MedDRA dictionary will be used for coding. Summaries will be
	provided using SOC and PT, where SOC will be sorted alphabetically and PT
	will be sorted in decreasing frequency.
	A subject with multiple occurrences of medical history or concurrent medical
	condition within a SOC will be counted only once in that SOC. A subject
	with multiple occurrences of medical history or concurrent medical condition
	within a PT will be counted only once in that PT.

1.2.3 Medication History and Concomitant Medications

Analysis Set: Analysis	Safety Analysis Set
2	
Variable(s) :	Medication History
	Concomitant Medications
Analytical	
Method(s):	(1) Medication History by Preferred Medication Name
	(2) Concomitant Medications That Started Prior to and Were Ongoing at
	Baseline as well as Those That Started After Baseline by ATC
	Pharmacological Subgroup and Preferred Medication Name
	Frequency distributions will be provided for each treatment group and
	overall. WHO Drug dictionary will be used for coding. Summaries will be
	provided using preferred medication names for (1) and using both ATC
	pharmacological subgroup and preferred medication names for (2). ATC

pharmacological subgroup will be sorted alphabetically and preferred medication names will be sorted in decreasing frequency based on the number of reports. A subject who has been administered several medications with the same preferred medication name will be counted only once for that preferred medication name.

1.3 Treatment Compliance

1.3.1 Study Drug Exposure and Compliance

Analysis Set:	Safety Analysis Set	
Analysis		
Variable(s) :	Duration of Exposure to Study Drug	[1<=-<=7, 8<=-<=14, 15<=-<=21,
	(days)	22<= - <=Max]
	Total Amount of Doses Taken (mg)	
	Dose Intensity (mg/day)	
	Relative Dose Intensity (%)	
	Subjects with Any Dose Held	[Yes, No]
	Reason for Dose Being Held	
	Adverse Event	[Yes]
	Other	[Yes]
	Dosing Compliance (%)	[Min<= - <=79.9, 80.0<= - <=89.9,
		90.0<= - <=Max]
Analytical		

 Method(s) :
 (1) Study Drug Exposure and Compliance

 Frequency distributions for categorical variables and descriptive statistics for continuous variables will be provided by treatment group and overall.

2 Study Subjects, Demographics, and Other Baseline Characteristics (Part B)

2.1 Disposition of Subjects

2.1.1 Screen Failures

Analysis Set: All Subjects Who Were Not Randomized

	Analysi	S
--	---------	---

Variable(s) :	Age (years)	[Min<= - <=64, 65<= - <=74,
		75<= - <=Max]
	Gender	[Male, Female]
Analytical		

Method(s): (1) Screen Failures Frequency distributions for categorical variables and descriptive statistics for continuous variables will be provided.

2.1.2 Subject Eligibility

Analysis Set:	All Subjects Who Signed the Informed Consent Form	
Analysis	Eligibility Status	[Eligible for Randomization, Not Eligible for
Variable(s) :		Randomization]
	Primary Reason for	[Pretreatment Event/Adverse Event, Major
	Subject Not Being Eligible	Protocol Deviation, Lost to Follow-Up,
		Voluntary Withdrawal, Study Termination,
		Did Not Meet Entrance Criteria, Other]

Analytical

Method(s): (1) Eligibility for Randomization

Frequency distributions will be provided. When calculating percentages for the primary reasons for subject not being eligible, the total number of ineligible subjects will be used as the denominator.

2.1.3 Number of Subjects Randomized by Site and Treatment Group

Randomized Set	
Randomization Status	[Randomized]
Site	[Site numbers will be used as categories]
(1) Number of Subjects Randomized	by Site and Treatment Group
Frequency distribution will be prov	ided for each stratum by treatment group
and overall.	
	Site (1) Number of Subjects Randomized Frequency distribution will be prov

2.1.4 Disposition of Subjects

Analysis Set:	Randomized Set	
	Subjects from the Randomized Set Who Completed Study Drug (48 Weeks)	
Analysis		
Variable(s) :	Study Drug Administration Status	[Randomized but Not Treated]
	Reason for Not Being Treated	[Pretreatment Event/Adverse Event,
		Major Protocol Deviation, Lost to
		Follow-Up, Voluntary Withdrawal,
		Study Termination, Lack of Efficacy,
		Other]
	Study Drug Completion Status (48	[Completed Study Drug (48 Weeks),
	Weeks)	Prematurely Discontinued Study
		Drug (48 Weeks)]
	Reason for Discontinuation of	[Pretreatment Event/Adverse Event,
	Study Drug	Major Protocol Deviation, Lost to
		Follow-Up, Voluntary Withdrawal,
		Study Termination, Lack of Efficacy,
		Other]
	Entrance into the Extension	[Entered the Extension Treatment
	Treatment Period	Period, Did Not Enter the Extension
		Treatment Period]
	Reason for Not Entering the	[Pretreatment Event/Adverse Event,
	Extension Treatment Period	Major Protocol Deviation, Lost to
		Follow-Up, Voluntary Withdrawal,
		Study Termination, Lack of Efficacy,
		Start of Other Treatment, Other]
	Study Drug Completion Status (96	[Completed Study Drug (96 Weeks),
	Weeks)	Prematurely Discontinued Study
		Drug (96 Weeks)]
	Reason for Discontinuation of	[Pretreatment Event/Adverse Event,
	Study Drug	Major Protocol Deviation, Lost to
		Follow-Up, Voluntary Withdrawal,
		Study Termination, Lack of Efficacy,
		Completed 48 Weeks of Treatment
		but Did Not Enter Extension, Other]

Completion Status of the Safety	[Completed Safety Follow-up,	
Follow-up	Prematurely Discontinued Safety	
	Follow-up]	
Reason for Discontinuation of the	[Pretreatment Event/Adverse Event,	
Safety Follow-up	Major Protocol Deviation, Lost to	
	Follow-Up, Voluntary Withdrawal,	
	Study Termination, Lack of Efficacy,	
	Other]	

Analytical

Method(s): (1) Disposition of Subjects

Randomized set will be used to perform the following analysis, with the exception of the summary for entrance into the extension treatment period and the reasons for not entering which will use subjects from the randomized set who completed study drug (48 weeks). Frequency distributions will be provided for each treatment group and overall. When calculating percentages for the reasons for not being treated, the total number of subjects not treated by the study drug will be used as the denominator. When calculating percentages for the reasons for discontinuation at 48 weeks and 96 weeks, the total number of subjects who prematurely discontinued the study drug before 48 weeks and 96 weeks (including subjects who completed 48 weeks of study drug treatment but did not enter the extension treatment period), respectively, will be used as the denominator. When calculating percentages for the reasons for the reasons for the reasons treatment period, the total number of subjects who completed 48 weeks of study drug treatment but did not enter the extension treatment period, the total number of subjects who completed 48 weeks of study drug treatment but did not enter the extension treatment period will be used as the denominator.

2.1.5 Study Drug Completion Status

Analysis Set:	Randomized Set	
Analysis	Study Drug Completion Status (96	[Completed Study Drug (96 Weeks),
Variable(s) :	Weeks)	Prematurely Discontinued Study
		Drug (96 Weeks)]
	Reason for Discontinuation of	[Pretreatment Event/Adverse Event,
	Study Drug	Major Protocol Deviation, Lost to
		Follow-Up, Voluntary Withdrawal,
		Study Termination, Lack of Efficacy,
		Completed 48 Weeks of Treatment
		but Did Not Enter Extension, Other]

Categories:	Duration of Exposure to Study Drug	[0<=-<=90, 91<=-<=180,
	(days)	181<= - <=270, 271<= - <=360,
		361<= - <=450, 451<= - <=540,
		541<= - <=630, 631<= - <=Max]

Analytical

Method(s) : (1) Study Drug Completion Status

> Frequency distribution will be provided for each category of duration of exposure to study drug by treatment group and overall.

2.1.6 Protocol Deviations and Analysis Sets

2.1.6.1 **Protocol Deviations**

Analysis Set: Randomized Set Analysis Variable(s) : **Protocol Deviation** [Major GCP Violations, Deviations of Protocol Entry Criteria, Deviations of Discontinuation Criteria, Deviations Related to Treatment Procedure or Dose, Deviations Concerning Excluded Medication or Therapy, Deviations to Avoid Emergency Risk] Analytical

Method(s) : (1) Protocol Deviations

Frequency distribution will be provided by treatment group and overall for each deviation category. A subject who has several deviations will be counted once in each appropriate category. A subject who has several deviations that can be classified into the same category will be counted only once.

2.1.6.2 Analysis Sets

Analysis	Randomized Set	
Set:		
Analysis		
Variable(s) :	Handling of Subjects and Subject Data	[Categories are based on the
		specifications in Handling Rules for
		Analysis Data]
	Analysis Sets	
	Full Analysis Set	[Included]
	Safety Analysis Set	[Included]
	Pharmacokinetic Analysis Set	[Included]

Analytical Method(s): (1) Subjects Excluded from Analysis Sets (2) Subject Data Excluded from Analysis Sets (3) Analysis Sets Frequency distributions will be provided by treatment group for (1) and (2) and by treatment group and overall for (3). For (1) and (2), a subject who has several reasons for exclusion will be counted once in each appropriate category. A subject who has several reasons for exclusion that can be classified into the same category will be counted only once.

2.2 Demographics and Other Baseline Characteristics

2.2.1 Summary of Demographics and Other Baseline Characteristics

Analysis Set:	Safety Analysis Set	
Analysis		
Variable(s) :	Age (years)	[Min<= - <=64, 65<= - <=74,
		75<= - <=Max]
	Gender	[Male, Female]
	Height (cm)	
	Weight (kg) (Week 0)	
	BMI (kg/m^2) (Week 0)	
	Smoking Classification	[The subject has never smoked,
		The subject is a current smoker,
		The subject is an ex-smoker]
	ECOG Performance Status (Week 0)	[0, 1, 2, 3, 4]
	Diagnostic Method	[Histological Diagnosis, Cytological
		Diagnosis, Other]
	Disease Duration (days)	
	Gleason Grading System (Gleason	[2, 3, 4, 5, 6, 7, 8, 9, 10]
	Score)	
	Histologic Type	[Adenocarcinoma, Other]
	Degree of Differentiation	[Well Differentiated
		Adenocarcinoma, Moderately
		Differentiated Adenocarcinoma,
		Poorly Differentiated
		Adenocarcinoma, Unclassified
		Adenocarcinoma]
	TNM Classification T	[T0, T1, T2, T3, T4, TX]

	TNM Classification N	[N0, N1, NX]
	TNM Classification M	[M0, M1, MX]
	Prostatectomy	[Yes, No]
	Radical Prostatectomy	[Yes, No]
	High-Intensity Focused Ultrasound	[Yes, No]
	Radiation Therapy	[Yes, No]
	Other Treatment	[Yes, No]
	PSA (ng/mL) (Week 0)	
	Testosterone (ng/mL) (Week 0)	
Analytical		
Method(s) :	(1) Summary of Demographics and Baseline Characteristics	
	Frequency distributions for categorica	l variables and descriptive statistics for
	continuous variables will be provided	by treatment group and overall.
2.2.2 Medical Hist	ory and Concurrent Medical Condition	ons
Analysis Set:	Safety Analysis Set	
Analysis		
Variable(s) :	Medical History	
	Concurrent Medical Conditions	
Analytical		
Method(s) :	(1) Medical History by System Organ Class and Preferred Term	
	(2) Concurrent Medical Conditions by	System Organ Class and Preferred
	Term	
	Frequency distributions will be provide	
	overall. MedDRA dictionary will be used for coding. Summaries will be	
	provided using SOC and PT, where SOC will be sorted alphabetically and PT	
	will be sorted in decreasing frequency.	
	5 1	of medical history or concurrent medical
	condition within a SOC will be count	
	•	history or concurrent medical condition
	within a PT will be counted only once	; iii uiat P I .
2.2.3 Medication History and Concomitant Medications		
Analysis Set:	Safety Analysis Set	
Analysis		

Variable(s) : Medication History Concomitant Medications

Analytical

Method(s): (1) Medication History by Preferred Medication Name

(2) Concomitant Medications That Started Prior to and Were Ongoing at Baseline as well as Those That Started After Baseline by ATC Pharmacological Subgroup and Preferred Medication Name
Frequency distributions will be provided for each treatment group and overall. WHO Drug dictionary will be used for coding. Summaries will be provided using preferred medication names for (1) and using both ATC pharmacological subgroup and preferred medication names for (2). ATC pharmacological subgroup will be sorted alphabetically and preferred medication names will be sorted in decreasing frequency based on the number of reports. A subject who has been administered several medications with the same preferred medication name will be counted only once for that preferred medication name.

2.3 Treatment Compliance

2.3.1 Study Drug Exposure and Compliance

v o	1 1	
Analysis Set: Analysis	Safety Analysis Set	
Variable(s) :	Duration of Exposure to Study Drug	[1<=-<=90, 91<=-<=180,
	(days)	181<= - <=270, 271<= - <=360,
		361<=-<=450, 451<=-<=540,
		541<= - <=630, 631<= - <=Max]
	Total Amount of Doses Taken (mg)	
	Dose Intensity (mg/day)	
	Relative Dose Intensity (%)	
	Subjects with Any Dose Held	[Yes, No]
	Reason for Dose Being Held	
	Adverse Event	[Yes]
	Other	[Yes]
	Subjects with Any Dose Reduction	[Yes, No]
	Reason for Dose Being Reduced	
	Adverse Event	[Yes]
	Other	[Yes]
	Dosing Compliance (%)	[Min<= - <=79.9, 80.0<= - <=89.9,
		90.0<= - <=Max]

Analytical

Method(s): (1) Study Drug Exposure and Compliance

Frequency distributions for categorical variables and descriptive statistics for continuous variables will be provided by treatment group and overall.

2.3.2 Dosing Pattern Details

Analysis Set:	Safety Analysis Set	
Analysis		
Variable(s) :	Dosing Pattern	[80 mg,
		120 mg,
		80 / 120 mg,
		80 / 120 / 80 mg,
		80 / 40 mg,
		120 / 160 mg,
		120 / 160 / 120 mg,
		120 / 80 mg, etc.]
		*These categories are merely an
		example and may change in
		accordance with the actual data.
	Last Dose	[40 mg, 80 mg, 120 mg, 160 mg]
Analytical		
Method(s):	(1) Dosing Pattern Details	

Frequency distributions will be provided by treatment group and overall.

3 Efficacy, Pharmacokinetic, and Pharmacodynamic Analysis (Part A)

3.1 Efficacy Analysis

3.1.1 Antitumor Effects

Analysis Set:	Full Analysis Set		
Analysis			
Variable(s) :	PSA (ng/mL)		
Visit :	Baseline, D28		
Analytical			
Method(s) :	The following analysis will be performed using the full analysis set.		
For the observed values, descriptive statistics and two-sided 95% con			
	intervals of the mean will be provided for each visit by treatment group. The		
	same analysis will be performed for the percent change from baseline.		

3.2 Pharmacokinetic Analysis

3.2.1 Plasma Concentrations

Analysis Set:	Pharmacokinetic Analysis Set		
Analysis			
Variable(s) :	Plasma concentrations of TAK-385 (ng/mL)		
Visit :	D1 and D14: Before dosing, 0.5, 1, 1.5, 2, 4, 6, 8 and 12 hours after dosing		
	D28: Before dosing, 1, 2, 4, 8, 12, 24, 48 and 72 hours after dosing		
	D3 and D7: Before dosing and 2 hours after dosing		
	D2, D12, D13, D15, D21 and D35: Before dosing		
Analytical	Number of subjects, mean, SD, min, median, max, geometric mean, and CV		
Method(s) :	will be used to summarize plasma concentrations at each visit for each		
	treatment group.		
	Linear plots of plasma concentration-time profiles will be provided for each		
	treatment group using individual and mean (SD) concentrations in separate		
	plots. Mean (SD) plots will include the plasma concentration plot for all		
	visits, separate plots for each of Day 1, Day 14, Day 28, and a plot for the		
	plasma trough concentrations.		

3.2.2 Pharmacokinetic Parameters

Listing			
Analysis Set:	Full Analysis Set		
Analysis			
Variable(s) :	D1: AUC _{τ} , C _{max} and t _{max}		
	D14: AUC _{last, ss} , AUC _{t, ss} , AUC _{t, ss} /D, C _{max, ss} , C _{max, ss} /D, C _{min, ss} , t _{max, ss}		

D28: AUC_{last, ss}, AUC_{τ , ss}, AUC_{τ , ss}/D, CL/F_{ss}, C_{max, ss}, C_{max, ss}/D, t_{max, ss}, t_{1/2z}, V_z/F_{ss}, λ_z , number of data points with first and last data points used in the terminal disposition phase regression analysis and adjusted R² (coefficient of determination) for the terminal disposition phase regression analysis

Analytical

Method(s): PK parameters will be calculated by using individual plasma concentrations with actual sampling times. Plasma concentrations from D1 to D2, D14 to D15 and D28 to D35 will be used for the calculation of PK parameters on D1, D14 and D28 respectively. Plasma concentrations deviated from the visit window will be also used for the calculation. A standard non-compartmental analysis will be performed using the linear trapezoidal rule. If subject received prohibited concomitant medications, therapies or foods, then the plasma concentrations measured on and after this day will be used to estimate the PK parameters for the listing but the results will be treated as reference values.

Individual PK parameters will be listed. The listings will include the treatment group, subject ID and evaluation day (D1, D14, and D28) in addition to the PK parameters.

Descriptive Statistics

Analysis Set:	Pharmacokinetic Analysis Set		
Analysis	D1:	AUC_{τ} , C_{max} and t_{max}	
Variable(s) :	D14:	$AUC_{last, ss}, AUC_{\tau, ss}, AUC_{\tau, ss}/D, C_{max, ss}, C_{max, ss}/D, C_{min, ss}, t_{max, ss}$	
	D28:	$AUC_{last, ss}, AUC_{\tau, ss}, AUC_{\tau, ss}/D, CL/F_{ss}, C_{max, ss}, C_{max, ss}/D, t_{max, ss} , t_{1/2z},$	
		$V_z/F_{ss}, \lambda_z$	

Analytical

Method(s) : For the pharmacokinetic parameters, the number of subjects, mean, SD, min, median, max, geometric mean, and CV will be provided for each treatment group. PK parameters which are treated as reference values will be excluded from the summary statistics.

Graphical assessment of dose-proportionality on $C_{max, ss}$ and $AUC_{\tau, ss}$ will be conducted on D14 and D28 by plotting individual dose-normalized exposure parameters, i.e., $C_{max, ss}/D$ or $AUC_{\tau, ss}/D$ versus dose.

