A number of cardiac AEs according to Common Terminology Criteria for Adverse Events (CTCAE) were reported, but for these subjects the ECG interpretation was considered to be not clinically significant by the investigator. These cardiac AEs included electrocardiogram QT prolonged (1 AE in Part 1, 4 AEs in Part 2, and 7 AEs in Part 3) and first degree atrioventricular block (2 AEs in Part 1 and 6 AEs in Part 2). Changes in mean QTc interval of approximately 15 to 20 msec were noted before administration on Day 14 (80 to 180 mg QD) in adult male subjects in this study. The QTc changes were independent of drug administration, not correlated to drug levels, and are similar to those observed in surgical and medical castration studies with other

compounds. No major safety concerns were noted in healthy male subjects receiving single (80 to 360 mg) and multiple (20 to 180 mg) doses of TAK-385, and TAK-385 was well tolerated.

Single doses of 80 to 360 mg of TAK-385 administered orally (fasted state) were absorbed rapidly in plasma with median Tmax values ranging from 1.75 to 4.00 hours after administration across the entire dose range. After attaining Cmax, TAK-385 plasma concentrations declined in a multi-exponential manner with a mean T1/2 ranging from 19.1 to 21.7 hours. The mean Cmax and AUC values for TAK-385 generally increased in an approximately dose-proportional manner over the 80 to 360 mg dose range.

When a multiple dose of 20 to 180 mg QD of TAK-385 was administered, the drug was readily absorbed in plasma on Days 1 and 14, and Cmax typically occurred within 1 to 2 hours after dosing. After attaining Cmax, individual PK profiles on Day 14 exhibited a multi-exponential elimination phase with a mean elimination phase T1/2 of approximately 36 to 65 hours at doses of 20 to 180 mg QD. The trough concentration-time data (Day 2, and Days 11 to 14) implied that steady-state conditions were attained within approximately 10 days.

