**Appendix D Schedule of Blood Samples Collection for Pharmacokinetic Analysis (Part A)**

Time Point a	Dosing Time Point b													
	D1	D2	D3	D7	D12	D13	D14	D15	D21	D28	D29	D30	D31	D35
Before dosing c	X	X	X	X	X	X	X	X	X	X	X d	X e	X f	X g
0.5 hour (± 10 min) postdose	X						X							
1 hour (± 15 min) postdose	X						X			X				
1.5 hours (± 15 min) postdose	X						X							
2 hours (± 20 min) postdose	X		X	X			X			X				
4 hours (± 20 min) postdose	X						X			X				
6 hours (± 30 min) postdose	X						X							
8 hours (± 30 min) postdose	X						X			X				
12 hours (± 1 hour) postdose	X						X			X				

Abbreviations: D = day

- 
- a If a blood sample is going to be collected on an outpatient basis, then the subject will come in for the visit without taking the study drug.
  - b As a rule, a blood sample will be collected at discontinuation as well, but the blood sample for the post-treatment observation period will not have to be collected.
  - c Blood samples for PK analysis will be collected within 1 hour before dosing.
  - d 24 hours (± 1 hour) after dosing on D28
  - e 48 hours (± 4 hours) after dosing on D28
  - f 72 hours (± 4 hours) after dosing on D28
  - g Collected before starting the next treatment

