 - AUC_{last, ss} --Area under the concentration-time curve from time 0 to time of the last quantifiable concentration, at steady state.
 - > AUC_{τ} --Area under the concentration-time curve during a dosing interval (= 24 hours).
 - > AUC_{τ , ss} --Area under the concentration-time curve during a dosing interval (= 24 hours), at steady state.
 - > AUC_{τ , ss}/D --Dose-normalized AUC_{τ}, at steady state.
 - CL/F_{ss} --Apparent clearance after extravascular administration, at steady state, calculated using AUC_τ.
 - ► C_{max} --Maximum observed concentration.
 - ➢ C_{max, ss} --Maximum observed concentration, at steady state.
 - \sim C_{max, ss}/D --Dose-normalized C_{max}, at steady state.
 - ► C_{min, ss} --Minimum observed concentration during a dosing interval, at steady state.
 - > λ_z --Terminal disposition phase rate constant.
 - > t_{max} --Time of first occurrence of C_{max} .
 - > $t_{max, ss}$ --Time of first occurrence of C_{max} , at steady state.
 - \blacktriangleright t_{1/2z} --Terminal disposition phase half-life.
 - V_z/F_{ss} --Apparent volume of distribution during the terminal disposition phase after extravascular administration, calculated using AUC_τ.

1 Study Subjects, Demographics, and Other Baseline Characteristics (Part A)

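### The linear trapezoidal rule across the 24 h and 96 h gaps after the last Part A dose overstates Day 28 AUClast,ss by about 3 to 7% when the Day 35 sample is quantifiable

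*SAP*

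**What the plan says.** SAP 3.2.2 (Part A pharmacokinetic parameters) sets one integration rule for every AUC: "A standard non-compartmental analysis will be performed using the linear trapezoidal rule". It gives no logarithmic option. The same section fixes the data span: "D28 to D35 will be used for the calculation of PK parameters on D1, D14 and D28 respectively".

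SAP 3.2.1 lists the sampling scheme as "D28: Before dosing, 1, 2, 4, 8, 12, 24, 48 and 72 hours after dosing", with a further sample on Day 35. The SAP visit-window table places that sample at 168 h after the Day 28 dose. Protocol Appendix D agrees on the last sample before it: "72 hours (± 4 hours) after dosing on D28".

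The list of PK parameters at the front of the SAP defines AUClast,ss as "Area under the concentration-time curve from time 0 to time of the last quantifiable concentration, at steady state". SAP 3.2.2 both lists and summarises it for Day 14 and Day 28. The same front list says that CL/F and Vz/F are calculated from AUCtau, the 24 h dosing-interval area. The dose-proportionality plots use dose-normalised Cmax,ss and AUCtau,ss.

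On the expected decline, Protocol 4.1.2.5 reports a multi-exponential profile on Day 14 in healthy men, with a "mean elimination phase T1/2 of approximately 36 to 65 hours at doses of 20 to 180 mg QD".

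**The concern.** The Day 28 profile has two 24 h gaps (24 to 48 h and 48 to 72 h) and one 96 h gap (72 to 168 h). All three fall after the last dose, when concentrations only decline. With the half-lives that the protocol reports, the 96 h gap spans about 1.5 to 2.7 half-lives (96/65 to 96/36). Over such a gap a straight line sits well above an exponential curve, so the linear rule always errs upward there.

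The bias is not a constant that cancels. It is larger for subjects who eliminate faster. It nearly disappears when the Day 35 concentration is below the quantification limit, because AUClast,ss then stops earlier. It can therefore differ between subjects in one cohort, and between cohorts if low-dose subjects more often fall below the limit by Day 35. What is at stake is the accuracy of one listed and summarised parameter. It is the only planned AUC that extends beyond the dosing interval.

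**Working it through.** The documents give no figure for AUC error, so there is no plan figure to reproduce.

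**Inputs from the documents**
- Integration rule: linear trapezoidal (SAP 3.2.2).
- Day 28 times: 0, 1, 2, 4, 8, 12, 24, 48, 72 h (SAP 3.2.1) and 168 h (SAP visit windows).
- Terminal half-life: 36 to 65 h (Protocol 4.1.2.5); 50 h is added as a midpoint.

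**Assumptions**
- The Day 35 sample is quantifiable, unless stated otherwise. The documents give neither an assay limit nor an expected 168 h concentration.
- Absorption rate and the size and speed of the distribution phase are not given. They were varied in the simulations below.

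**Step 1: error within one gap.** For an exponential decline with rate k = ln 2 / half-life over a gap d:

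- linear area = d(C1 + C2)/2
- true area = (C1 − C2)/k
- linear/true = (kd/2) · coth(kd/2)

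Example, 36 h half-life and 96 h gap: k = 0.01925 per h, kd/2 = 0.9242, tanh(0.9242) = 0.7279, ratio = 0.9242/0.7279 = 1.270, or +27.0%.

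**Step 2: weight by each gap's share of AUC(0–168).** For a single exponential the share of 24 to 72 h is (e^(−24k) − e^(−72k))/(1 − e^(−168k)); 72 to 168 h is analogous. At 36 h: (0.630 − 0.250)/(1 − 0.039) = 0.396, and (0.250 − 0.039)/(1 − 0.039) = 0.219.

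| Half-life | Error per 24 h gap | Error in 96 h gap | Share 24–72 h | Share 72–168 h | Effect on AUClast,ss |
|---|---|---|---|---|---|
| 36 h | +1.77% | +26.97% | 0.396 | 0.219 | 0.70 + 5.91 = +6.6% |
| 50 h | +0.92% | +14.34% | 0.386 | 0.300 | 0.36 + 4.31 = +4.7% |
| 65 h | +0.55% | +8.58% | 0.372 | 0.357 | 0.20 + 3.06 = +3.3% |

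**Step 3: simulated steady-state oral profiles.** Sampling at the planned times and comparing with a fine-grid integral gave the same one-compartment results: +6.6%, +4.7% and +3.3%. Two-exponential shapes gave +5.5 to +6.6% (36 h), +4.3 to +5.2% (50 h) and +3.2 to +4.1% (65 h). Across three absorption rates the range was +2.8% to +6.7%. Linear-up/log-down on the same samples gave −1.1% to +1.1%.

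**Step 4: last quantifiable sample at 72 h.** The one-compartment error falls to +0.88% (36 h) and +0.28% (65 h). Across shapes with a distribution phase it was about +0.2% to +4.3%.

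**Step 5: the 24 h parameters.** Day 28 AUCtau under the linear rule was −0.3% to +2.6%. That error comes from sampling within the first 24 h, not from the late gaps.

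**Step 6: candidate fixes.** Using the log rule only for declining intervals after 24 h left Day 28 AUClast,ss between −0.1% and +2.6%. What remains comes from the first 24 h and from any distribution phase that persists after it. Using linear-up/log-down for all AUCs could move Day 28 AUCtau down to −2.0% when absorption is fast.

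**The case against.** The strongest reply is that nothing planned depends on the affected number. AUClast,ss is listed and summarised, with no test and no comparison. Cohort advancement rests on dose-limiting toxicities, each cohort has 3 or 6 subjects, and the output is descriptive. The secondary endpoint is plasma concentration, which no integration rule alters, and Part B plans no AUC. The linear rule is a recognised, prespecified choice, and nothing in the documents contradicts it. All of this stands, and it limits the importance of the point. It does not make the Day 28 figure right.

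A reader might infer more than the documents support in four ways:

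- **That CL/F, Vz/F and dose proportionality inherit the bias.** They do not. They rest on the 24 h area or on Cmax,ss, and their small error has a different source.
- **That 3 to 7% is unconditional.** It needs a quantifiable Day 35 sample and a half-life taken from healthy men, not from these patients. In extreme shapes (very high peak-to-trough ratio, fast absorption), missed area around the peak offsets part of it and the net error falls to about 1.4 to 3%. At the protocol's single-dose half-lives of 19.1 to 21.7 h, it would be about 8.5%.
- **That the SAP hides the different Day 14 and Day 28 spans.** Both spans are stated in SAP 3.2.2, no comparison of AUClast,ss between the days is planned, and AUCtau,ss is given on both days over a common 24 h.
- **That linear-up/log-down should replace the linear rule for every AUC.** With fast absorption this can slightly worsen AUCtau, the area that feeds CL/F and Vz/F.

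**Conclusion.** The concern holds for Day 28 AUClast,ss in Part A only. With a quantifiable Day 35 sample and a terminal half-life of 36 to 65 h, the linear rule overstates it by about 3 to 7%, mostly from the 72 to 168 h gap. With 72 h as the last quantifiable sample, the error is about 0 to 4%. The direction is systematic and the size depends on the subject's half-life and on Day 35 quantifiability. Absorption and distribution shape are assumptions, and the ranges reflect varying them. AUCtau,ss, CL/F, Vz/F and the dose-proportionality plots are not materially affected. No primary endpoint or dose decision turns on the point. It is a minor improvement worth making because it is almost free.

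**What to change.** In SAP 3.2.2, specify the logarithmic trapezoidal rule for declining intervals after 24 h on Day 28, and keep the linear rule for AUCtau on all days. An acceptable alternative is linear-up/log-down for Day 28 AUClast,ss alone. Either way AUCtau,ss, CL/F, Vz/F and the dose-proportionality plots are unchanged.

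Optionally, add a table footnote that Day 28 AUClast,ss extends beyond the dosing interval and is not comparable with the Day 14 value under the same symbol.

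The cost is one SAP sentence and one software setting, with no new samples. Protocol 13.1.4 asks only for a model-free analysis, so no protocol amendment is needed. The downside is that Day 28 AUClast,ss becomes slightly less comparable with earlier studies that used the linear rule throughout.
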